3.1 Purpose

3.1.1 Main purpose

The main objective of this study was to investigate the rate of lower alveolar nerve injury 1 month after endoscopy combined with intraoperative navigation-assisted treatment of giant mandibular cyst.

3.1.2 Secondary Purpose

The secondary objective of this study was to investigate the recurrence rate 1 year after endoscopy combined with intraoperative navigation-assisted treatment of giant mandibular bone cysts.

3.1.3 Exploratory purpose

The exploratory objective of this study was to evaluate the postoperative efficacy of endoscopy combined with intraoperative navigation-assisted treatment of giant mandibular bone cysts

3.2. Research indicators

3.2.1 Main Indicators and Definitions

Rate of inferior alveolar nerve injury 1 month after surgery: For patients who received endoscopic combined with intraoperative navigational assistance in the treatment of giant mandibular cyst, inferior alveolar nerve function was detected before surgery and 1 month after surgery to determine whether postoperative inferior alveolar nerve injury existed. Detailed detection methods are shown below.

3.2.2 Secondary indicators and definitions

Recurrence rate 1 year after surgery: The number of patients who received endoscopy combined with intraoperative navigation-assisted treatment for giant mandibular bone cysts who had cyst recurrence 1 year after surgery.

3.2.3 Security Specifications

The subjects' vital signs, blood routine, liver function, heart function, blood biochemistry, urine routine, stool routine, coagulation function, electrocardiogram, chest film, maxillofacial imaging data and other safety indicators were all interpreted by the researcher team based on the test results before the subjects were enrolled.

IV. Study the population

4.1 Inclusion criteria

- (1) Aged between 18 and 75 years old
- (2) Imaging and puncture pathology showed dental cystic lesions of the mandible
- (3) Cystic lesions greater than or equal to 2cm in diameter and affecting the inferior alveolar nerve
- (4) Lesions of new or recurrent cysts, or odontogenic cystic lesions that are still greater than or equal to 2cm after other treatments such as fenestration and affecting the lower alveolar nerve
- (5) No serious systemic diseases, can tolerate general anesthesia
- (6) Patients who intend to undergo surgical treatment for mandibular bone cysts under general anesthesia
- (7) There was no inferior alveolar nerve injury before operation
- (8) Did not participate in other clinical trials within the past 30 days
- (9) Patients who voluntarily participate in the project and sign informed consent

4.2 Exclusion Criteria

- (1) The patient has serious systemic disease or pregnancy, and after the research team and multidisciplinary consultation and evaluation, it is determined that she cannot tolerate the clinical study process and general anesthesia
- (2) Unable to complete the entire clinical research process due to personal, social and economic reasons
- (3) Patients suffering from mental diseases or unable to perceive and communicate normally, such as schizophrenia, claustrophobia, etc., are unable to complete the examination and cooperate with the entire clinical study process

4.3 Lifestyle considerations

After entering the clinical study, the subjects should have a light diet, abstain from tobacco and alcohol, and prohibit strenuous exercise. If the subjects need to use drugs, treatments or operations unrelated to the study in the clinical study, the researchers should evaluate whether the reasons for the need for such drugs, treatments and surgical treatments are adverse events caused by the study. If the subject needs additional treatment due to accident or other reasons, whether the

treatment has an impact on the progress of the study will be considered. If the impact is too large, it is recommended that the subject withdraw from the conventional treatment and seal the subject's data.

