5.4.2 Data Analysis Set

Statistical analysis will be performed using SAS statistical analysis software (V.9.4, SAS Institute). If there is no special explanation, unilateral test will be used for the main index, and the control error α is 0.025; bilateral test will be used for the other indicators, and the error α is =0.05. If you need to calculate confidence intervals, calculate bilateral 95% confidence intervals unless otherwise specified.

- (1) full analysis set (FAS) : comprised of all subjects who underwent surgical treatment and were evaluated for efficacy. The data set is derived from all subjects by eliminating subjects in a minimal and reasonable way.
- (2) safety analysis set (SS) : A group of people who have received surgical treatment and have safety evaluation data. In the safety analysis, all patients will be analyzed according to the actual surgical group received.
- (3) per-protocol set (PPS) : all subjects who met the protocol and did not use concomitant drugs that affected the effectiveness evaluation, had good medication compliance (between 80% and 120%), and excluded subjects who had a major protocol violation and were judged to have a significant impact on the results. All trial protocol deviations that result in subjects being excluded from the conformance protocol set will be detailed in the Statistical Analysis Plan (SAP) and completed prior to data locking.

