The processing principle of missing/deleted/lost data: LOCF (last observation carried forward) method was adopted to fill in the analysis of main indicators, that is, the last observed data was used to fill in the data that failed to observe the main indicators. Secondary indicators and security indicators are not filled.

VI. Research and intervention

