7.2 Subject discontinuation/withdrawal from study

When subjects suspend or withdraw from the study due to dissatisfaction with the therapeutic effect of the study program or their own financial reasons, they should communicate with them to encourage them to actively treat the treatment and help them apply for public welfare funds to complete the treatment. In the perioperative period, if serious complications of anesthesia, serious postoperative infection or bleeding, respiratory distress caused by severe edema of surrounding tissues, nerve tears and other serious complications reached 30% of the number of subjects, the study should be suspended, and the safety of the surgical method of the study protocol should be discussed to determine whether to adjust the study surgical protocol, and follow-up should be conducted during the suspension of the study. Follow-up records of the original subjects were maintained. In the case of clear withdrawal, the investigator may continue to complete the follow-up without the study intervention.

7.3 Loss of access (measures to reduce loss of access and data loss due to loss of access)

After the enrollment of subjects, the researchers should keep the contact information of multiple subjects and the contact information of subjects' families. After the subjects are discharged from hospital, the researchers should actively contact the subjects by phone, timely understand the condition of the subjects, and arrange the subjects to be admitted to the hospital for the next stage of treatment in advance.

VIII. Adverse Events and unexpected events

An adverse event (AE) is an adverse medical event that occurs after a subject receives treatment, but is not necessarily causally related to the treatment. An adverse event may be any adverse and unexpected sign (including abnormal laboratory findings), symptom, or disease associated with the use of the treatment, regardless of whether it is related to the treatment. It includes, but is not limited to:

- (1) exacerbation of disease that existed before the study treatment was used;
- (2) Increased frequency or severity of paroxysmal events that existed before the study treatment was used;
- (3) abnormal changes detected or diagnosed after the study of treatment use, although such abnormal changes may have existed before treatment;
- (4) Exacerbation of disease or symptoms that were already persistent before the study began.

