Causal relationship between adverse events and treatment measures: In the trial, researchers should conduct comprehensive analysis according to the specific

circumstances of adverse events and subjects' past history, concomitant diseases and concomitant medication, etc., to determine the relationship between adverse events and treatment measures. The relationship between adverse events and treatment measures was classified as "definitely related, it may well be relevant, it may be relevant, it may not be relevant and it may not be relevant."

- (1) Unrelated: Adverse events were not associated with treatment.
- (2) May not be relevant: the occurrence of an adverse event is more likely to be related to other factors, such as co-medication or concomitant disease, or the timing of the event indicates that it is unlikely to be causally related to the treatment.
- (3) May be related: The occurrence of adverse events may be caused by therapeutic measures. Cannot rule out whether other Causes, such as: drug combination or concomitant disease. The occurrence of adverse events and treatment measures have a reasonable time sequence, and the causal relationship between the events and treatment measures cannot be ruled out.
- (4) Likely related: The occurrence of adverse events may be caused by therapeutic measures. The occurrence and treatment measures are Reasonable chronological order.
- (5) Definitely relevant: the type of adverse event has been identified as a result of the treatment and cannot be otherwise justified

Explain, for example, drug combinations and concomitant diseases. The timing of the event strongly suggests causality. The criteria for judging the severity of adverse events can refer to the following criteria:

- (1) Mild: mild symptoms or signs but tolerable.
- (2) Moderate; Symptoms are significant enough to interfere with normal life.
- (3) Severe: severe symptoms, has been unable to carry out normal activities.

All information about adverse events, whether referred to by the patient, discovered by the investigator, or discovered by physical examination, laboratory examination, etc., should be recorded in the study medical record and case report form. During the trial, the occurrence time, duration, symptoms, signs and severity, measures taken and outcome of adverse events should be carefully observed and recorded

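### Section 4.3 recommends sealing some patients' data with no criterion, time limit or definition, which does not fit the analysis sets or the follow-up allowed after withdrawal

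*Protocol*

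**What the plan says.** Protocol section 4.3 applies once a subject has entered the study. If additional treatment is needed because of an accident or for some other reason, its effect on the progress of the study is to be weighed. Then: "If the impact is too large, it is recommended that the subject withdraw from the conventional treatment and seal the subject's data". No threshold, decision-maker or time window is given, and sealing is not defined.

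Other parts of the protocol bear on the same patients:

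- **FAS (5.4.2).** It is "comprised of all subjects who underwent surgical treatment and were evaluated for efficacy", and "The data set is derived from all subjects by eliminating subjects in a minimal and reasonable way".
- **SS (5.4.2).** It is "A group of people who have received surgical treatment and have safety evaluation data".
- **Withdrawal (2.2.1 item 4, and 7.2).** "In the case of clear withdrawal, the investigator may continue to complete the follow-up without the study intervention".
- **Missing primary data (end of 5.4.3).** Last observation carried forward (LOCF) is used: "the last observed data was used to fill in the data that failed to observe the main indicators".
- **Baseline (4.1, item 7).** Patients must have no inferior alveolar nerve injury before surgery.
- **Timing (5.2.1 and 5.2.3).** The nerve is tested before surgery and at 1 month only. Surgery is the day after the enrolment visit, and the schedule runs to 1 year.

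**The concern.** Almost all the time during which section 4.3 can apply lies after surgery. The trial has one arm, and the protocol states no blinded assessment, so those who judge the impact may know how the patient is doing. The same paragraph asks whether a need for unrelated treatment stems from an adverse event caused by the study, so outcome-related treatment is not clearly outside its reach.

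If sealing means that the data are not used, an operated patient can be lost on a discretionary judgement made after treatment. For a patient sealed before the 1-month test there are two routes. Either the patient was never evaluated for efficacy and leaves the FAS, or LOCF fills the gap from a baseline that is uninjured by design. Both hide an injury if there was one. A patient sealed after that test could be chosen with the result known. Where sealing is linked to a bad outcome, the injury rate is biased downwards in favour of the new procedure. Recurrence and adverse event rates could be affected in the same way.

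**Working it through.** **1. The plan's own figure.** Inputs: historical rate p0 = 0.32 (8/25, section 2.1), expected rate p1 = 0.20 (section 5.1), one-sided alpha 0.025, power 80%, dropout 10% (section 5.4.1).

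n = [(1.960 × √(0.32 × 0.68) + 0.842 × √(0.20 × 0.80)) / 0.12]² = 108.67, so 109; 109 / 0.90 = 121.1, so 122.

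Both stated figures reproduce. The sealing clause does not touch the sample size.

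**2. Success rule used.** The exact 95% upper limit must lie below 32%, which is a one-sided exact test at 0.025. Section 5.4.3 names the lower limit; that is a separate matter. The largest number of injuries that still succeeds is 28 of 122, 26 of 116 and 25 of 110.

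**3. False-positive rate when the true rate is 32%.** Assume 122 operated, k sealed, and an injury rate q among the sealed. Neither k nor q is in the protocol.

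- Sealed patients excluded: rate in the rest = (122 × 0.32 − kq) / (122 − k).
- Sealed patients carried forward as uninjured: observed rate = (122 × 0.32 − kq) / 122.

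The chance of success is the binomial probability of a count at or below the limit in step 2, at that rate.

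| k | q | Rate in the rest | Excluded | Carried forward as uninjured |
|---|---|---|---|---|
| 0 | – | 32.0% | 0.018 | 0.018 |
| 6 | 32% | 32.0% | 0.015 | 0.042 |
| 6 | 50% | 31.1% | 0.025 | 0.065 |
| 6 | 75% | 29.8% | 0.049 | 0.111 |
| 12 | 32% | 32.0% | 0.021 | 0.088 |
| 12 | 50% | 30.0% | 0.056 | 0.178 |
| 12 | 75% | 27.3% | 0.166 | 0.379 |

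Example, k = 12 and q = 75%: (39.04 − 9) / 110 = 27.3%, and P(25 or fewer of 110) = 0.166. Twelve sealed is 12/122 = 9.8%, close to the planned dropout.

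With exclusion, sealing unrelated to outcome (q = 32%) does not inflate the error. With LOCF it does even then, because every sealed patient counts as uninjured.

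**4. Could a single result change?** With 30/122 injured (24.6%) the exact upper limit is 33.2%, so the trial fails. Seal 6, of whom 4 are injured: 26/116 (22.4%) has an upper limit of 31.1% and succeeds. If only 3 of the 6 are injured, 27/116 has an upper limit of 32.03% and still fails. Near the planned rate, 24/122 (19.7%) has an upper limit of 27.8% and succeeds with nobody sealed.

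**The case against.** A reader might infer that section 4.3 tells sites to withdraw every patient who needs additional treatment, and that this removes operated patients from the efficacy and safety analyses. The text does not go so far:

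- Withdrawal is only recommended, and only where the impact is judged too large. The literal wording, withdrawal from conventional treatment, is unclear in a single-arm trial and may be a translation fault.
- Section 4.3 names neither the FAS nor the SS. Section 5.4.2, read alone, keeps an operated patient who has the relevant data, and lists neither sealing nor withdrawal as a ground for exclusion.
- Re-operation, infection and bleeding are not named in 4.3. Severe infection, bleeding and failed repair of a torn nerve have their own rule in 2.2.1 item 4, which says nothing of sealing.
- Section VIII says that adverse event information "should be recorded in the study medical record and case report form". Data can be recorded and then sealed, so there is no strict conflict. Follow-up under 7.2 is optional.
- Nothing says that sealed data are destroyed or cannot be reopened.
- The numerical harm needs sealing to be linked to outcome, or LOCF to be applied.

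All of these points stand, and they limit the finding. They do not remove it. An instruction to seal data, with no criterion and no definition, remains open to the harmful reading. It is a stated rule, not a detail left for a later analysis plan. The separate rule in 2.2.1 adds a further difficulty, since the protocol does not say which rule governs a patient who falls under both.

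**Conclusion.** The point holds in a limited form. Section 4.3 contains a discretionary sealing rule that can be applied after surgery. On its natural reading it cannot be reconciled with the FAS and SS definitions or with the follow-up allowed after withdrawal. That operated patients will be dropped from the analyses is an inference from an undefined word and should not be stated as the protocol's rule. Nor do the documents support the view that the loss would be beyond correction.

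The size is conditional on the assumed number sealed and their injury rate. With exclusion, the false-positive rate ranges from no inflation (sealing unrelated to outcome, or 6 sealed with half injured, about 0.025) to about 0.166 (12 sealed, 75% injured). Carrying sealed patients forward as uninjured is worse in every case calculated. The protocol gives no basis for choosing among these cases. This should be fixed, but it does not by itself invalidate the design.

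**What to change.** Delete the sealing clause from section 4.3 and state instead:

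- additional treatment and its reason are recorded;
- all data already collected are kept, and operated patients stay in the FAS and SS;
- the 1-month nerve test, recurrence imaging and adverse event collection continue unless the patient withdraws consent;
- any removal is from the per-protocol set (PPS) only, decided before data lock and without reference to the nerve-test result.

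Reconcile section 4.3 with 2.2.1 item 4 and 7.2, so that one data-handling rule applies to a given patient. When treatment should stop, or a patient should withdraw, is a clinical matter for the sponsor and is not judged here.

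The cost is a few sentences of protocol wording and no new procedure. The downside is some heterogeneity in the FAS from patients who had extra treatment, which the PPS analysis can show.

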4.4 Filtering Failure

Patients will be screened after signing the informed consent for this study, and those who fail the screening will be excluded from the study. Based on the results of the multidisciplinary consultation, the study will inform the failed patients and give the optimal treatment recommendations.

4.5 Recruitment and retention strategies

This study will recruit subjects mainly offline and combine both online and offline. The main offline location will be the Oral and maxillofacial Surgery Department of Sun Yat-sen Memorial Hospital, including but not limited to posters, leaflets, information sessions and other forms to attract more subjects. Every interested patient will register on the spot, leave his contact information and continue to have one-to-one explanation program. If the subject has financial difficulties, the researcher team will assist the subject to apply for public welfare fund to help reduce the financial burden of the subjects.

V. Research design

5.1 Overall Design

This study hypothesized that endoscopy combined with intraoperative navigation-assisted treatment of giant mandibular bone cysts was more effective than the traditional surgical method of removal and curettage. In this study, a prospective, single-arm, Phase II clinical study was used to design the protocol, and the estimated rate of postoperative nerve injury was reduced by about 12% from 32% to 20% compared with traditional surgery.

5.2 Research and design process

5.2.1 Study the specific implementation process

This study started from the recruitment of subjects, oral panoramic film, maxillofacial CT and other imaging examinations were performed to confirm the diagnosis. After preliminary screening according to the inclusion and exclusion criteria, patients were enrolled after signing the informed consent letter. Endoscopic and navigational techniques were used for surgical treatment. This study referred to A prospective study by Abdullah Hanfesh¹⁵ et al to evaluate the function of the inferior alveolar nerve: the bilateral mandibular and lower lip were divided into four areas: area A, area B, area C, and area D. The four areas will be lightly touched, acupuncture, cold and hot stimulation, and two-point discrimination detection four times respectively. The detection situation of each area will be recorded. The scoring criteria for each test are as follows.

[figure not shown]

Figure 1. Area diagram¹⁵
 A: Upper right lip B: Upper left lip C: Right jaw D: Left mandible

Light touch: Cotton wool is used for light touch detection. The score range is 0-4, with 4 indicating no nerve damage.

Table 1 Light touch stimulus rating table

Sign	Score
Completely unresponsive to stimuli	0
Severe loss of perception	1
Mild irritation is almost imperceptible	2
Compared with pre-operation slight stimulation can still be perceived	3
Compared with pre-operation there was no difference, normal perception of mild stimulation	4

Acupuncture: Detection is performed using dental probe stimulation on a scale of 0-1, with 1 indicating no nerve damage.

Table 2. Acupuncture stimulation rating table

Sign	Score
Completely unresponsive to stimuli	0
Produces a sharp tingling sensation to stimuli	1

Figure 2 Lower alveolar nerve function measured by cotton wool¹⁵

Figure 3. The function of inferior alveolar nerve was detected by acupuncture¹⁵

Hot and cold stimulation: Test tubes filled with hot water (45-50 ° C) and filled with ice water were used to detect hot and cold stimulation, respectively. The score range was 0-1, with 1 indicating no nerve damage.

Table 3. Cold and heat stimulation rating table

Sign	Score
Completely unresponsive to stimuli	0
Develop a cold/hot sensation to stimuli	1

Figure 4. The function of inferior alveolar nerve was measured by heat and cold stimulation¹⁵

Two-point discrimination test: The distance between two points can be distinguished using a vernier caliper. The score ranges from 0 to 5, with 5 indicating no nerve damage.

Table 4: Two-point discrimination measurement rating table

Sign	Score
The distance between the two ends of the vernier caliper is > 15mm	0
The distance between the ends of the vernier caliper is 10-15mm	1
The distance between the ends of the vernier caliper is 9-10mm	2
The distance between the ends of the vernier caliper is 7-9mm	3
The distance between the ends of the vernier caliper is 5-7mm	4
The distance between both ends of the vernier caliper is less than 5mm	5

Figure 5 Vernier calipers measure the distance between two points¹⁵

Inferior alveolar nerve function was detected before and 1 month after surgery. Light touch detection 4 points, acupuncture detection 1 point, hot and cold stimulation 1 point, two-point discrimination detection 5 points showed no nerve damage. Any other score for any of the above is considered to be nerve damage.

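### The pinprick and thermal scales cannot carry out the rule that any shortfall is nerve injury: hot and cold share one point, and a dull pinprick response has no score

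*Protocol*

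**What the plan says.** Protocol 5.2.1 sets out four sensory tests in four areas of the lower lip and jaw, done before surgery and at one month.

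- **Thermal (Table 3).** A tube of hot water and one "filled with ice water were used to detect hot and cold stimulation, respectively". One scale follows: "The score range was 0-1, with 1 indicating no nerve damage". Score 0 is "Completely unresponsive to stimuli" and score 1 is "Develop a cold/hot sensation to stimuli".
- **Pinprick (Table 2).** "Detection is performed using dental probe stimulation on a scale of 0-1, with 1 indicating no nerve damage". Score 0 has the same anchor as in Table 3; score 1 is "Produces a sharp tingling sensation to stimuli".
- **Light touch (Table 1) and two-point discrimination (Table 4).** These are graded 0-4 and 0-5, and only the top level counts as no damage. The two highest levels of Table 1 are worded as a comparison with the preoperative state.
- **Injury rule (end of 5.2.1).** Among the maxima required are "hot and cold stimulation 1 point, two-point discrimination detection 5 points showed no nerve damage". Any other score on any test counts as nerve damage.

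Section 3.2.1 makes the resulting one-month injury rate the primary indicator. Section 5.1 describes a single-arm trial that expects a fall from 32% to 20%.

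**The concern.** The injury rule is strict: anything short of a full score is injury. It works only if every form of partial loss produces a score below the maximum. Tables 1 and 4 meet that condition. Tables 2 and 3 do not, because their only score below the maximum is anchored at total loss.

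For temperature the gap runs one way, towards fewer recorded injuries. For pinprick it leaves the assessor to choose, and the protocol describes no blinded assessor. The trial has no concurrent arm in which the same scoring would apply, so under-recording is set against a fixed historical 32% and favours the new procedure. The preoperative test uses the same scales, so a partial deficit at baseline could also pass inclusion criterion 7 (section 4.1), which requires no nerve injury before surgery.

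**Working it through.** **1. Responses set against the anchors**

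| Response in one area | Fits score 0? | Fits score 1? | Result |
|---|---|---|---|
| Neither hot nor cold felt | yes | no | 0, counted as injury |
| Hot felt, cold not (or the reverse) | no, there is a response | yes, if cold/hot means either | can be 1, no damage |
| Both felt, but weakly | no | yes | can be 1, no damage |
| Pinprick not felt | yes | no | 0, counted as injury |
| Pinprick felt as dull pressure | no | no, not sharp | undefined |
| Pinprick felt as sharp | no | yes | 1, no damage |

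Complete loss of pinprick, or of both thermal senses, is recorded correctly. The gaps are rows 2, 3 and 5.

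**2. One thermal score or two?** Table 3 does not say whether both sensations are needed. The injury rule asks for a single point for hot and cold together, whereas two separate 0-1 scores would need two points. That favours one shared score.

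**3. When the gap reaches the endpoint.** A patient is misclassified only if every other test is at its maximum: light touch 4 (no difference from before surgery) and two-point discrimination 5 (under 5 mm) in the tested areas. What escapes is an isolated partial deficit of temperature or pain sense.

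**4. The plan's sample size, reproduced.** Inputs: p0 = 0.32 and p1 = 0.20 (section 5.1); one-sided alpha 0.025 and power 80% (section 5.4.1).

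n = [(1.960 × √(0.32 × 0.68) + 0.842 × √(0.20 × 0.80)) / 0.12]² = [(0.914 + 0.337) / 0.12]² = 108.7, so 109.

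With 10% dropout, 109 / 0.90 = 121.1, so 122. Both stated figures reproduce. The scoring gap alters neither.

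**5. Illustration of sensitivity.** At n = 109 the exact one-sided binomial test of 32% at 0.025 succeeds with 25 or fewer injuries: P(X ≤ 25 | 0.32) = 0.0246, whereas P(X ≤ 26 | 0.32) = 0.0401. Suppose the true rate is 32% and a share of all patients is injured but scored as undamaged. The share is assumed; the protocol gives no figure for it.

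| Share missed (assumed) | Recorded rate | P(X ≤ 25) |
|---|---|---|
| 0 points | 32% | 2.5% |
| 1 point | 31% | 4.0% |
| 2 points | 30% | 6.4% |
| 5 points | 27% | 20.0% |

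The table shows how the false-success probability responds to under-recording. It does not estimate how much under-recording these tables would cause.

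**The case against.** The strongest reply concerns the thermal test. The two tubes are applied respectively, so Table 3 could be meant for each tube in turn: cold felt from the cold tube, hot from the hot tube, each scored 0-1. A patient who feels nothing from the ice tube would then score 0 and count as injured. The wording allows this, but the single point in the injury rule goes against it. Even on that reading, a weak but present sensation still scores 1.

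Second, four tests in four areas, two of them graded, will catch many partial losses. This stands and confines the problem to isolated deficits.

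Third, two-level pinprick and thermal scales are a legitimate choice, and the assessment follows a published method that is not reproduced in full. This also stands. The fault is not that the scales have two levels, but that the levels do not cover all responses or match the protocol's own rule.

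A reader might infer three stronger things that the protocol does not support:

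- *That pinprick has the same fault as temperature.* It does not. A dull response fails the sharp anchor, and nothing in the text sends it to score 1.
- *That the recorded rate will be low by some stated number of points.* The protocol contains nothing from which to derive that number, and a dull pinprick response would not always be scored 1.
- *That one misclassified patient would reverse the conclusion.* The upper Clopper-Pearson limit is 31.97% for 25/109 and 32.97% for 26/109, but a one-patient switch exists at the threshold of any binary endpoint. Section 5.4.3 also words its criterion on the lower limit (15.4% and 16.2% here), under which both counts would pass. That wording is a separate matter.

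**Conclusion.** The point holds as a defect in the definition of the primary endpoint. Tables 2 and 3 do not implement the rule that any shortfall on any test is injury. For temperature, the more natural reading lets the loss of one of hot and cold, or a weakened sense of either, be scored as no damage, and this error can only lower the recorded rate. For pinprick, a dull response has no defined score and the result depends on the assessor.

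The effect is limited to patients whose light touch and two-point scores are perfect in the tested areas, and its size is unknown. The rise from 2.5% to 6.4% rests on an assumed 2 points missed, a true rate of 32%, 109 analysed patients and a threshold of 25 injuries. It is a reason to close the gap, not evidence of how wide it is.

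**What to change.** - **Table 3:** score hot and cold separately, 0 or 1 each.
- **Injury rule at the end of 5.2.1:** require hot 1 point and cold 1 point, both needed for no nerve damage.
- **Tables 2 and 3:** let score 0 cover every response other than the sensation that defines score 1 (for pinprick, anything not felt as sharp), judged against the preoperative test as Table 1 already does.

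This should be settled before outcomes are scored, because a one-sided thermal response or a dull pinprick response stored as 1 cannot be recovered later.

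The cost is revised table wording and one extra CRF field per area; both stimuli are already applied. The recorded injury rate may rise slightly. That matters because the 32% benchmark (8 of 25 patients, section 2.1) is described as symptoms of nerve damage and not as a result of this test battery, so a more complete battery makes the comparison somewhat harder on the new procedure. The protocol should acknowledge this when it makes the change.
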